9.3.4.1.2. Grading of Laboratory Abnormalities

Only abnormal labs that are clinically significant, per the judgement of the investigator, should be reported as treatment-emergent adverse events, which should be graded based on the clinical scenario. Further, the grading of these adverse events should be based on guidance provided in protocol Section 9.3.4.1 for events not included in the protocol-defined grading system.

Tables 10 (serum chemistry), 11 (hematology) and 12 (urinalysis) present FDA toxicity grading information for vaccine studies, which include guidance to consider institutional normal ranges in determining lab toxicity grade. These ranges may be utilized by the Sponsor when evaluating any overall trends in lab abnormalities observed across study (sites and central labs) but should not be utilized when reporting clinically significant unsolicited AEs. Only post-screening safety laboratory tests will have toxicity grades assessed in Part 1 analysis. Post-screening abnormal lab results with toxicity grade 3 or above that are not deemed clinically significant by the investigator and not captured as adverse events will be displayed separately in the clinical study report.

	Mild	Moderate	Severe	Potentially Life Threatening
Serum ^a	(Grade 1)	(Grade 2)	(Grade 3)	(Grade 4)
Sodium – Hyponatremia mEq/L	132 to 134	130 to 131	125 to 129	< 125
Sodium – Hypernatremia mEq/L	144 to 145	146 to 147	148 to 150	> 150
Potassium – Hyperkalemia mEq/L	5.1 to 5.2	5.3 to 5.4	5.5 to 5.6	> 5.6
Potassium – Hypokalemia mEq/L	3.5 to 3.6	3.3 to 3.4	3.1 to 3.2	< 3.1
Glucose – Hypoglycemia mg/dL	65 to 69	55 to 64	45 to 54	< 45
Glucose – Hyperglycemia				Insulin
Fasting – mg/dL	100 to 110	111 to 125	>125	requirements or
Random – mg/dL	110 to 125	126 to 200	>200	hyperosmolar com
BUN mg/dL	23 to 26	27 to 31	> 31	Requires dialysis
Creatinine – mg/dL	1.5 to 1.7	1.8 to 2.0	2.1 to 2.5	> 2.5 or requires dialysis
Calcium – hypocalcemia mg/dL	8.0 to 8.4	7.5 to 7.9	7.0 to 7.4	< 7.0
Calcium – hypercalcemia mg/dL	10.5 to 11.0	11.1 to 11.5	11.6 to 12.0	> 12.0
Magnesium – hypomagnesemia mg/dL	1.3 to 1.5	1.1 to 1.2	0.9 to 1.0	< 0.9
Phosphorous – hypophosphatemia mg/dL	2.3 to 2.5	2.0 to 2.2	1.6 to 1.9	< 1.6
CPK – mg/dL	1.25 to 1.5 x ULN	1.6 to 3.0 x ULN	3.1 to 10 x ULN	> 10 x ULN
Albumin – Hypoalbuminemia g/dL	2.8 to 3.1	2.5 to 2.7	< 2.5	
Total Protein – Hypoproteinemia g/dL	5.5 to 6.0	5.0 to 5.4	< 5.0	
Alkaline phosphate – increase by factor	1.1 to 2.0 x ULN	2.1 to 3.0 x ULN	3.1 to 10 x ULN	> 10 x ULN
Liver Function Tests – ALT, AST increase by factor	1.1 to 2.5 x ULN	2.6 to 5.0 x ULN	5.1 to 10 x ULN	> 10 x ULN
Bilirubin – when accompanied by any increase in Liver Function Test increase by factor	1.1 to 1.25 x ULN	1.26 to1.5 x ULN	1.51 to 1.75 x ULN	> 1.75 x ULN
Bilirubin – when Liver Function Test is normal; increase by factor	1.1 to 1.5 x ULN	1.6 to 2.0 x ULN	2.0 to 3.0 x ULN	> 3.0 x ULN
Cholesterol	201 - 210	211 - 225	> 226	
Pancreatic enzymes – amylase, lipase	1.1 to 1.5 x ULN	1.6 to 2.0 x ULN	2.1 to 5.0 x ULN	> 5.0 x ULN

ULN = upper limit of normal

^a The laboratory values provided in the tables serve as guidelines and are dependent upon institutional normal parameters.

Institutional normal reference ranges should be provided to demonstrate that they are appropriate. Refer to section 9.3.4.1.2.

	Mild	Moderate	Severe	Potentially Life Threatening
Hematology ^a	(Grade 1)	(Grade 2)	(Grade 3)	(Grade 4)
Hemoglobin (Female), gm/dL	11.0 to 12.0	9.5 to 10.9	8.0 to 9.4	< 8.0
Hemoglobin (Female) change from baseline value, gm/dL	Any decrease to 1.5	1.6 to 2.0	2.1 to 5.0	> 5.0
Hemoglobin (Male), gm/dL	12.5 to 13.5	10.5 to 12.4	8.5 to 10.4	< 8.5
Hemoglobin (Male) change from baseline value, gm/dL	Any decrease to 1.5	1.6 to 2.0	2.1 to 5.0	> 5.0
WBC increase, cell/mm ³	10,800 to 15,000	15,001 to 20,000	20,001 to 25,000	> 25,000
WBC decrease, cell/mm ³	2,500 to 3,500	1,500 to 2,499	1,000 to 1,499	< 1,000
Lymphocytes decrease, cell/mm ³	750 to 1,000	500 to 749	250 to 499	< 250
Neutrophils decrease, cell/mm ³	1,500 to 2,000	1,000 to 1,499	500 to 999	< 500
Eosinophils, cell/mm ³	650 to 1500	1501 to 5000	> 5000	Hypereosinophilic
Platelets Decreased, cell/mm ³	125,000 to 140,000	100,000 to 124,000	25,000 to 99,000	< 25,000
PT, increase by factor	1.0 to 1.10 x ULN	1.11 to 1.20 x ULN	1.21 to 1.25 x ULN	> 1.25 ULN
PTT, increase by factor	1.0 to 1.2 x ULN	1.21 to 1.4 x ULN	1.41 to 1.5 x ULN	> 1.5 x ULN
Fibrinogen increase, mg/dL	400 to 500	501 to 600	> 600	
Fibrinogen decrease, mg/dL	150 to 200	125 to 149	100 to 124	< 100 or associated with gross bleeding or DIC

Table 11Grading of Laboratory Abnormalities (Hematology)

DIC = disseminated intravascular coagulation; PT = prothrombin time; PTT = partial thromboplastin time; ULN = upper limit of normal; WBC = white blood cell

^a The laboratory values provided in the tables serve as guidelines and are dependent upon institutional normal parameters. Institutional normal reference ranges should be provided to demonstrate that they are appropriate. Refer to section 9.3.4.1.2

Table 12 Grading of Laboratory Abnormalities (Urinalysis)

Urine*	Mild (Grade 1)	Moderate (Grade 2)	Severe (Grade 3)	Potentially Life Threatening (Grade 4)
Protein	Trace	1+	2+	Hospitalization or dialysis
Glucose	Trace	1+	2+	Hospitalization for hyperglycemia
Blood (microscopic), red blood cells per high power field	1 to 10	11 to 50	> 50 and/or gross blood	Hospitalization or packed red blood cells transfusion

^a The laboratory values provided in the tables serve as guidelines and are dependent upon institutional normal parameters. Institutional normal reference ranges should be provided to demonstrate that they are appropriate. Refer to section 9.3.4.1.2

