3.2.2. Part 1: Eligibility for Second Vaccination

At the Week 4 visit participants will have safety assessments to evaluate suitability to receive the second vaccination including physical exam, vital signs, pregnancy test (female participants), SARS-CoV-2 rapid molecular test, and assessment of adverse events and new concomitant medication usage. Participants meeting any of the following exclusion criteria will not be eligible to receive their second vaccine administration:

Exclusion Criteria for Second Vaccine Dose:

• Positive pregnancy test at Day 29 (female participants),

Version 5.0

- Occurrence of any possibly, probably or definitely treatment-related Grade 3 or 4 AE or SAE following the initial vaccination
- Occurrence of any Grade 3 or 4 AE or SAE following the initial vaccination without plausible alternative explanation
- Presence of acute illness or significant new medical condition including positive SARS-COV-2 rapid molecular test prior to dosing

Participants deemed ineligible due to presence of acute illness or new medical condition may be re-assessed during the visit window (+7 days), and if the condition resolves, may receive their second vaccination within 1 week of their scheduled Week 4 Visit. In such situations the Principal Investigator must contact the study Medical Monitor and gain consensus on the decision to continue participant with study vaccinations prior to administration of the second dose.

Upon completion of the study Active Period (Week 8 Visit) participants will enter the Safety Follow-up Period and be monitored for SAEs, MAAEs and for exposure to and/or symptomatic COVID-19, including the potential for VAED, through the Month 13/End of Study (EOS). In addition, these participants will be evaluated for immunogenicity as specified in the SoA (Table 3). During the Safety Follow-up Period participants will return to the site at Months 7 and 13 for safety monitoring and collection of samples for evaluation of immunogenicity; they will also be contacted by phone monthly between site visits to query for safety and exposure to and/or symptomatic COVID-19.

Any participant who discontinues study drug early (does not receive the second dose) will enter the Safety Follow-up Period a month earlier at Week 4 and will be monitored for safety and exposure to and/or symptomatic COVID-19 as described above, and complete immunogenicity assessments through EOS per the SoA (Table 3).

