6.1.1. Part 1 Halting Rules

- 1. Any participant experiences a vaccine-related SAE.
- 2. Two or more participants experience the same or similar Grade ≥3 solicited AE (first and second vaccinations to be assessed separately).
- 3. Two or more participants experience the same or similar Grade ≥3 unsolicited single AE preferred term or clinical laboratory AE which the investigator assesses as possibly, probably or definitely related to study vaccine.
- 4. Occurrence of severe COVID-19 in any participant as defined below. If this halting rule is met, all available clinical, nonclinical safety and immunogenicity data will be reviewed by the IDMC to evaluate for potential vaccine enhanced COVID-19.

Per FDA's June 2020 Guidance Development and Licensure of Vaccines to Prevent COVID-19, severe COVID-19 disease is defined as virologically confirmed SARS-CoV-2 infection with any of the following:

- a. Clinical signs at rest indicative of severe systemic illness (respiratory rate ≥30 beats per minute, heart rate > 125 per minute, peripheral hemoglobin oxygen saturation [SpO₂] <93% on room air at sea level or partial pressure of oxygen [PaO₂]/fraction of inspired oxygen [FiO₂] < 300 mm Hg)
- Respiratory failure (defined as needing high-flow oxygen, noninvasive ventilation, mechanical ventilation or extracorporeal membrane oxygenation [ECMO])
- c. Evidence of shock (Systolic blood pressure < 90 mm Hg, diastolic blood pressure <60 mm Hg, or requiring vasopressors)
- d. Significant acute renal, hepatic, or neurologic dysfunction
- e. Admission to an intensive care unit (ICU)
- f. Death

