6.1.2. Part 2 Halting Rules

- 1. Any participant experiences a vaccine-related SAE.
- 2. Five or more participants experience the same or similar Grade ≥3 solicited AE (first and second vaccinations to be assessed separately).
- 3. Five or more participants experience the same or similar grade ≥3 unsolicited single AE preferred term or clinical laboratory AE which the investigator assesses as possibly, probably or definitely related to study drug administration.
- 4. Occurrence of severe COVID-19 in any participant, per the definition above, and IDMC determines there is evidence of vaccine enhanced COVID-19. If this halting rule is met, all available clinical and preclinical safety and immunogenicity data will be reviewed by

the IDMC to evaluate for potential vaccine enhanced COVID-19.

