7.2.3. Clinical Safety Laboratory Assessments

- See Appendix 2 (Section 9.2) for the list of clinical laboratory tests to be performed and to the SoA for the timing and frequency.
- The Investigator must review the laboratory report, document this review, and record any clinically relevant changes occurring during the study in the AE section of the eCRF. The laboratory reports must be filed with the source documents.
- All laboratory tests with values considered clinically significant during participation in the study or within 14 days after the last dose of study drug should be repeated

until the values return to normal or baseline or are no longer considered clinically significant by the Investigator or Sponsor's Medical Monitor (or designee). If such values do not return to normal/baseline within a period of time judged reasonable by the Investigator, the etiology should be identified, and the Sponsor notified.

- Laboratory values which are abnormal AND lead to either the requirement for an intervention, the requirement for additional medications, or are felt to otherwise be medically important should be recorded as adverse events in the eCRF. Only abnormal labs that are clinically significant, per the judgement of the investigator, should be reported as treatment-emergent adverse events, which should be graded based on the clinical scenario. Further, the grading of these adverse events should be based on guidance provided in protocol Section 9.3.4.1 Grading the Severity of TEAEs.
- Hematology or serum chemistry parameters will be graded according to the FDA toxicity grading scale (Section 9.3.4.1.2) and will be adjusted to align with local laboratory reference ranges (Part 1 only) for clinically significant abnormal laboratory tests. Subjects have the ability to rescreen once should screening values fall outside of the allowed eligibility criteria, per the discretion of the Investigator. Post-screening abnormal lab results with toxicity grade 3 or above that are deemed not clinically significant by the investigator and not captured as adverse events will be included separately in the clinical study report.
- Pregnancy testing should include serum hCG at screening. Negative urine pregnancy test should be confirmed on Days 1 and 29 prior to dosing..

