9.3.4.1. Grading the Severity of TEAEs

Assessment of Severity

All TEAEs will be assessed by the investigator using a protocol-defined grading system. For events not included in the protocol-defined grading system, the following guidelines will be used to quantify severity:

Mild: events require minimal or no treatment and do not interfere with the participant's daily activities.

Moderate: events result in a low level of inconvenience or concern with the therapeutic measures. Moderate events may cause some interference with functioning.

Severe: events interrupt a participant's usual daily activity and may require systemic drug therapy or other treatment. Severe events are usually incapacitating.

Life threatening: any adverse drug experience that places the participant, in the view of the investigator, at immediate risk of death from the reaction as it occurred, i.e., it does not include a reaction that had it occurred in a more severe form, might have caused death.

Changes in the severity of an AE should be documented to allow an assessment of the duration of the event at each level of intensity to be performed. Adverse events characterized as intermittent require documentation of onset and duration of each episode.

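### Sections 7.2.3 and 9.3.4.1.2 grade hematology and chemistry AEs on different scales; under 9.3.4.1.2 a related, symptom-free Grade 3 value can be called Mild and miss halting rule 3 and the graded second-dose stop

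*Combined protocol and SAP*

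**What the plan says.** **Section 7.2.3** has two adjacent bullets. The first says only clinically significant abnormal results become AEs, to be graded from the clinical picture under 9.3.4.1. The second says "Hematology or serum chemistry parameters will be graded according to the FDA toxicity grading scale", adjusted to the local reference range, and ends by tying this to clinically significant abnormal tests.

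**Section 9.3.4.1** offers its functional scale as a fallback: "For events not included in the protocol-defined grading system, the following guidelines will be used to quantify severity". Mild means "events require minimal or no treatment and do not interfere with the" participant's day-to-day activity. Severe means that normal activity is interrupted.

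**Section 9.3.4.1.2** sends laboratory AEs to that fallback scale, although Tables 10 to 12 do grade laboratory values. It leaves the tables to the sponsor's review of trends and says they "should not be utilized when reporting clinically significant unsolicited AEs". Values of Grade 3 or above that are neither judged clinically significant nor recorded as AEs are shown separately in the study report.

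**Halting rule 3.** In Part 1 (6.1.1) the trigger is two or more participants with the same or a similar Grade 3 or higher "unsolicited single AE preferred term or clinical laboratory AE which the investigator assesses as possibly, probably or definitely related to study vaccine". In Part 2 (6.1.2) it is "Five or more participants experience the same or similar grade ≥3 unsolicited single AE preferred term or clinical laboratory AE", again with relatedness required.

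**Second dose.** Sections 3.2.2 and 4.2.2 exclude on "Occurrence of any possibly, probably or definitely treatment-related Grade 3 or 4 AE or SAE following the initial vaccination". They also have an ungraded criterion, "Presence of acute illness or significant new medical condition".

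Neither rule 3 nor the second-dose criteria say which scale supplies the grade.

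**The concern.** Rule 3 is the pre-set stop for repeated related laboratory toxicity. It is useful because it fires on a count, without anyone having to decide that a pattern is worrying. That requires two sites seeing the same result to record the same grade, and here they need not.

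The two scales measure different things: one the size of the abnormality, the other its effect on daily life and its treatment. Laboratory toxicity is often silent, so a functional scale is a poor trigger for a laboratory stop. Thrombocytopenia makes a natural example because it is part of a risk named in 2.3.1, and a low count can exist before any symptom.

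**Working it through.** No power or alpha figure is involved. The check compares texts, looks up tables and counts.

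**1. Table grade.** Table 11, platelets per mm³: Grade 1 is 125,000 to 140,000; Grade 2 is 100,000 to 124,000; Grade 3 is 25,000 to 99,000; Grade 4 is below 25,000. Counts of 25,000, 50,000 and 99,000 are all Grade 3.

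**2. The same case on both scales.** Take a count of 60,000 that is judged related and clinically significant, is untreated and causes no symptoms.

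| | Table 11 (second bullet of 7.2.3) | 9.3.4.1 (via 9.3.4.1.2) |
|---|---|---|
| Grade | 3 | fits Mild |
| Adds to rule 3 | 1 | 0 |
| Graded second-dose exclusion, if after Dose 1 | met | not met |
| Part 1 rule 3 with two such participants | 2: halt for IDMC review | 0: no halt |

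A count that needed more than minimal treatment would not fit Mild.

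**3. Is it only platelets?** Rows of Tables 10 and 11 that match the Table 8 analytes drawn after dosing:

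- Table 10: sodium 2, potassium 2, low glucose 1, high random glucose 1, BUN 1, creatinine 1, ALT/AST 1, bilirubin 2. Sum = 11.
- Table 11: hemoglobin 4, white cells 2, platelets 1. Sum = 7.
- Total 11 + 7 = 18. All 18 set Grade 3 by a laboratory value; none uses activity or treatment.

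Coagulation rows are left out (screening only), as are white-cell differential rows (Table 8 does not say whether a differential is done). Urinalysis is left out because the FDA-scale sentence in 7.2.3 covers hematology and chemistry only.

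**4. Where it can happen.** Table 3 schedules safety laboratory tests after Dose 1 on Days 8, 29, 36 and 57. With full attendance that is 4 × 72 = 288 draws in Part 1. Table 4 schedules none after screening in Part 2.

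**5. Illustration under assumed rates.** The documents give no incidence. Let p be the assumed true rate of related Table 11 Grade 3 counts among n = 72 independent participants, and s the share graded below Severe. With q = p(1 − s):

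P(rule 3 fires) = 1 − (1 − q)^72 − 72q(1 − q)^71.

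| p (assumed) | s = 0 | s = 0.5 | s = 1 |
|---|---|---|---|
| 1% | 0.16 | 0.05 | 0 |
| 2% | 0.42 | 0.16 | 0 |
| 3% | 0.64 | 0.29 | 0 |
| 5% | 0.88 | 0.54 | 0 |

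This shows how far the rule depends on the choice of scale. It does not forecast that such events will occur.

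**The case against.** **The texts can be reconciled.** The second bullet of 7.2.3 speaks of parameters and cites 9.3.4.1.2, so it can be read as concerning values for analysis, while AEs are graded clinically. The summary of Amendment 4 in 9.7 shows that clinical grading was intended. This largely stands as a reading, though the closing words of the 7.2.3 sentence point to the very results that become AEs. It does not remove the consequence: if the functional scale governs, the silent low count is Mild and rule 3 misses it.

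**Severe already means Grade 3.** The table headers pair the two, so the missing numbers in 9.3.4.1 are a small gap. This stands. The problem is what Severe requires, not how it is numbered.

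**Other routes catch thrombocytopenia.** A reader might infer that such a count would pass unnoticed or could not stop dosing. The documents do not support that. Section 9.3.3 gives blood dyscrasias as an example of events usually considered serious. One related SAE halts the study under rule 1, which is stricter than rule 3, and also bars the second dose. The ungraded second-dose criterion, expedited AESI reporting (9.5), the Medical Monitor's review of laboratory results (8.5.1) and the IDMC (8.5.2) remain. All of this stands, but none of these routes is automatic on the count. Rule 3 also needs judgement, on significance and relatedness; the functional scale adds a further condition unrelated to the size of the abnormality.

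**Little is left to protect.** A reader might infer a broad exposure in Part 2. Table 4 rules that out, leaving unscheduled tests. Part 1 dosing may also be complete. The IDMC review before Part 2 is still ahead, however, and the separate listing in 9.3.4.1.2 covers only values not captured as AEs. A Grade 3 value recorded as a Mild AE falls outside it.

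**A blanket table rule would go too far.** Taking the higher grade for every analyte in Tables 10 to 12, and for every second dose, would partly undo the choice of clinical grading. A related potassium of 5.5 called significant would then bar Dose 2. This stands, and the fix is narrower.

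**Conclusion.** The point holds in a limited form. The sections conflict on how clinically significant hematology and chemistry AEs are graded. On the 9.3.4.1.2 reading, the laboratory part of rule 3 turns on interference with daily activity, so a related, untreated, symptom-free Table 10 or 11 Grade 3 value can go uncounted there and in the graded second-dose stop.

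The size is a tally of 2 against 0 in a constructed Part 1 case, with the same mismatch across all 18 relevant table rows. It assumes that investigators apply the Mild definition as written; the probabilities also rest on assumed rates. No efficacy estimate or error rate changes.

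The practical reach is Part 1 and the IDMC's review before Part 2. The change should be made before the Part 2 dose is chosen. Confidence is medium, because the alternative routes may work well in practice.

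**What to change.** 1. **7.2.3 and 9.3.4.1.2:** keep clinical-scenario grading for the AE severity field, make 7.2.3 say so, and limit the bar on the tables to that field.
2. **6.1.1 and 6.1.2, rule 3:** for a hematology or chemistry AE judged clinically significant and related, count the Table 10 or 11 grade adjusted to the laboratory's reference range, or the 9.3.4.1 severity (Severe or worse) if that is higher.
3. **3.2.2 and 4.2.2:** apply the same grade to the second-dose exclusion at least for platelets, with a low count confirmed on repeat. The NaCitrate platelet test could serve; the protocol names it for eligibility, so post-dose use would be an extension.
4. **Before Part 2 dose selection:** give the IDMC the Part 1 laboratory AEs with their Table 10 or 11 grades, alongside the listing of Grade 3 or higher values not recorded as AEs.

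**Cost.** Wording in six sections and one listing from data already collected. No scheduled visit is added; a repeat sample is needed only when a platelet count is low. The downside is a somewhat higher chance of a reversible pause for IDMC review, or of a withheld second dose, on a symptom-free laboratory AE. The clinical-significance and relatedness conditions limit that.

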9.3.4.2. Assessment of Causality

Assessment of Causality

- For all solicited symptoms and unsolicited TEAEs, including SAEs and MAAEs, the Investigator will make a judgment regarding the relationship of the AE to the study vaccine. All TEAEs must be recorded in the source documents as well as eCRF.
- A "reasonable possibility" of a relationship conveys that there are facts, evidence, and/or arguments to suggest a causal relationship, rather than a relationship cannot be ruled out.
- The investigator will use clinical judgment to determine the relationship.
- Alternative causes, such as underlying disease(s), concomitant therapy, and other risk factors, as well as the temporal relationship of the event to study intervention administration will be considered and investigated.
- The investigator will also consult the Investigator's Brochure (IB) and/or Product Information, for marketed products, in his/her assessment.
- For each TEAE/SAE, the investigator **must** document in the medical notes that he/she has reviewed the TEAE/SAE and has provided an assessment of causality.
- There may be situations in which an SAE has occurred, and the investigator has minimal information to include in the initial report to the Sponsor. However, it is very important that the investigator always make an assessment of causality for every event before the initial transmission of the SAE data to the Sponsor.
- The investigator may change his/her opinion of causality in light of follow-up information and send an SAE follow-up report with the updated causality assessment.
- The causality assessment is one of the criteria used when determining regulatory reporting requirements.

The relationship of the AE to study vaccine administration will be specified as follows:

Not related:	In the Investigator's opinion, there is no causal relationship between study vaccine administration and the TEAE;
Possibly Related:	The TEAE follows a reasonable temporal sequence from the time of study vaccine administration but there may be another equally likely explanation for the event (e.g., the participant's clinical state or other medications);
Probably Related:	The TEAE follows a reasonable temporal sequence from the time of study vaccine administration and cannot be reasonably explained by the known characteristics of the participant's clinical state;
Definitely Related:	The TEAE follows a known temporal sequence from the time of study vaccine administration, cannot be explained by other disease or medications and the event is an objective and specific medical disorder or a recognized pharmacological phenomenon.

